## **5.7 Study Interventions (12 weeks' duration)**

**Arm 1:** EGCG: 800mg EGCG +250mg VitC taken 1 time a day. Subjects will a bag with 84 light resistant pill pouches. Each pill pouch will contain four 200mg EGCG capsules with one 250mg VitC tablet. Subjects will be instructed to take all the contents of each pill pouch every day at breakfast for a period of 12 weeks. Subjects will be monitored monthly for hepatotoxicity (liver function test of ALT, AST, and bilirubin). Subjects will receive a weekly phone call to assess any safety concerns and to assess adherence.

**Arm 2:** Usual care – Subjects will be assigned to usual care during the course of the study. Subjects will receive a weekly phone call as a check in.

## **5.8 Study Drug**

Patients will be randomized to one of two treatment arms. Encapsulated EGCG will be supplied by Teavigo. No subject identifiable data will be shared with Teavigo. Each capsule will contain on average 200mg EGCG (94%). Four 200mg EGCG capsules will be packaged with one 250mg VitC tablet and labelled at the pharmacy core at the University of Rochester Medical Center Investigational Drug Service ([name]) into a light resistant pill pouch. At the time of randomization, study personnel will provide subjects with a bag with the 84 pill pouches, the twelve week supply of the study supplement. Instructions on how to correctly take the study drug will be given and reviewed with subjects in Arm 1. Subjects in Arm 1 will be instructed to start taking the study drug on day 1. The study drug will be stored in a secured location within the Cancer Control Unit at URMC that is locked at all times and only accessible by approved study personnel.

## **5.9 Intervention contact and tracking**

The study coordinator will make every effort to contact each subject 1 time per week via phone calls, and/or emails, (based on each subject's preference) to encourage intervention adherence to the study drug. During this weekly contact the study coordinator will also ask about any safety concerns including: symptoms, signs, illnesses, or experiences, that develop or worsen during the study. These concerns will be graded (according to the CTCAE v5.0 see section 7), recorded, reviewed with the treating oncologist as well as the medical monitor, and reported (if necessary) according to the outline in section 7. If medical information needs to be further discussed, we will set up a phone call, virtual meeting or face-to-face meeting. Study contact will occur from our research staff, which includes study PI, the study staff (coordinators, etc.), and the patient's treatment team (e.g., oncologists, nurses, staff, etc.).

Subjects in the intervention arm will report to URMC labs at weeks four and eight after baseline for a lab draw to determine liver function (ALT, AST, and bilirubin) so that any hepatotoxicity can be monitored. Study personnel will call subjects to remind and coordinate the blood draws.

To track adherence, we will instruct subjects to bring all remaining study drug at their post-intervention assessment (T2) and the pills will be manually counted and pill counts will be entered onto the pill excel document.

## **5.10 Post-intervention assessment (T2)**

The post-intervention assessment will follow the same format as the baseline assessment (T1) with the addition of Fried's frailty measures from screening assessment (T0). In addition, we will also ask subjects to complete the following:

### *Secondary Aim 1: Pill count form*

Subjects will be instructed to return any remaining study drug at their post-intervention (T2) visit. All remaining study drug will be counted by research staff and pill counts will be used to determine adherence to study measures.

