## **5.2 Timing of assessments**

Screening assessment T0 must be completed no more than 10 years after the completion of subject's curative intent cancer treatment. This timing is to ensure that lasting effects of curative intent cancer treatment immune system are minimized and that frailty is still likely to be present. This time frame is also consistent with other survivorship clinical trials.

Assessments T0 and T1 can be completed on the same day. In the event that assessment T0 and T1 are completed on different days, assessment T1 should not occur more than 4 weeks after T0. If for some reason T1 occurs more than 4 weeks after T0, Fried's frailty measures must be repeated to ensure that subjects still meet eligibility criteria. Optimally, assessments T0 and T1 will occur on the same day or within 1 week.

Optimally, assessment T2 will occur during week 13 (within the first week after the completion of study drug), but this may be adjusted (for to no more than 3 weeks after the completion of the study drug) to accommodate factors such as the clinical, subject, and researcher's schedule.

The following table details the approximate study timeline.

Table 1: Approximate study timeline															
Study week		0	1	2	3	4	5	6	7	8	9	10	11	12	13
Study activities	Consent T0	T1*													T2

\*Optimally T1 occurs within 1 week after T0 or on the same day.

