### *Exploratory Aim 3: Semi-structured interviews:*

We will conduct semi-structured interviews with subjects at the post-intervention assessment (T2). Questions in the interview will be structured in a way to gain insights into the frailty experience of older survivors of colorectal cancer post adjuvant treatment. Interviews will be audio recorded and transcribed verbatim. Interviews with the subjects will be held in person in a private space (clinic or office space). Interviews will be audio-recorded and led by study investigators and will last 30 minutes. These recordings will be uploaded to Box, and the recordings will be deleted from the audio-recorder. All interviews will be transcribed and qualitatively analyzed in an iterative process until theoretical saturation is achieved.

We will also ask subjects about the usefulness and acceptability of the study treatments during the close out interview. The post intervention visit and measures may be completed in person, via phone and/or Zoom.

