### 11.1 Sample size determination

We plan to enroll 40 subjects (20;  $\geq 6$  AA/B per arm). Evaluation of recruitment and adherence to the intervention is required for planned future Phase 2/3 frailty trials in older cancer survivors.

*Aim 1:* With a feasibility target of 70% of

Protocol Date: January 2016

44

randomized subjects completing the study we expect at least 14 evaluable patients per arm, which is appropriate for small randomized studies and it will allow us to obtain preliminary estimates of descriptive statistics (mean, standard deviation (SD), and confidence intervals (CI)). *Aim 2:* At significance level  $\alpha=0.15$ ,  $N=14$  per arm will provide 70% power to detect effect size (standardized mean change in frailty score) of 0.66, if pre-post correlation=0.5 (conservative estimate for FFS; Figure 5).

**Analyses:** *Aim 1:* For each feasibility outcome (recruitment and adherence), we will evaluate proportions of subjects meeting criterion and report percentages with CIs. For AEs, we will report the total and severity of AE's per group. *Aim 2:* Descriptive statistics will be calculated at baseline, post-intervention, and for pre-post change scores for subjects in EGCG and UC arms. To evaluate the preliminary efficacy estimates of EGCG on FFS we will use an analysis of covariance (ANCOVA) model (outcome=FFS at post, covariates: FFS at baseline and arm). Estimates of distribution characteristics (e.g., mean, variance, pre-post correlation) and preliminary estimates of efficacy will inform the design and sample size of our planned future study. *Aim 3:* Similar analyses to Aim 2 will be performed for TNF- $\alpha$ , TNFRI, TNFRII, IL-6, IL-1 $\beta$ , and CRP. If data for inflammatory markers are missing due to lower limit of detection, we will use appropriate imputation methods. *Aim 4:* Using similar analyses to Aim 2, we will conduct preliminary subgroup analyses by race and treatment type.

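### The only quantified measure of EGCG adherence is one count of leftover pouches at T2, which cannot separate lost leftovers or late doses from full intake on schedule

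*Combined protocol and SAP*

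**What the plan says.** Section 2.3 places adherence to the EGCG intervention under Aim 1. Section 11.1 gives the analysis: "For each feasibility outcome (recruitment and adherence), we will evaluate proportions of subjects meeting criterion". No criterion for adherence is stated there or elsewhere.

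Under sections 5.7 and 5.8 the whole supply of 84 pouches is handed over at randomization, and one pouch is to be taken "every day at breakfast for a period of 12 weeks". Section 5.9 says: "To track adherence, we will instruct subjects to bring all remaining study drug at their post-intervention assessment (T2", followed by a manual count. The pill count form in section 5.10 adds: "All remaining study drug will be counted by research staff and pill counts will be used to determine adherence to study measures".

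Two other sources bear on exposure. For Arm 1, section 5.7 says: "Subjects will receive a weekly phone call to assess any safety concerns and to assess adherence". Section 5.3 maps the weekly phone call log to Aim 1, as it does the pill count form. Section 5.5 measures serum EGCG once, at T2, without calling it an adherence measure.

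On timing, section 5.2 aims for T2 in week 13 but lets it move, "for to no more than 3 weeks after the completion of the study drug". On format, section 5.10 says: "The post intervention visit and measures may be completed in person, via phone and/or Zoom". Section 11.2 sets complete case as the general rule for missing data, apart from biomarker values below the detection limit.

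**The concern.** Because there is no overage and only leftovers are requested, a fully adherent subject has nothing to bring back. A subject who left unused pouches at home or threw them away also brings back nothing, and the form records the two alike. No scoring rule chosen later can repair this. If an empty return means zero left, some non-adherent subjects count as adherent. If it means missing, the most adherent subjects drop out of the estimate.

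The count is also tied to the T2 visit and not to day 84. Subjects keep their leftovers until T2 and no last-dose date is recorded, so doses taken after week 12 can offset earlier misses.

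Section 11.1 says the evaluation of adherence is required for the planned later trials. With about 14 evaluable subjects in the EGCG arm, a few ambiguous returns can settle the result. The same record would be used to judge whether a small frailty difference reflects the supplement or doses not taken.

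**Working it through.** **Inputs from the protocol.** Supply: 84 pouches (5.7, 5.8). Dosing: daily for 12 weeks (5.7). T2: within the first week after the drug ends, or up to 3 weeks after (5.2). Evaluable subjects: at least 14 per arm (11.1).

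**The plan's own figures.** 12 × 7 = 84, so supply equals scheduled doses exactly. 0.70 × 20 = 14 evaluable per arm. Both reproduce.

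**Assumption.** The protocol gives no adherence formula. The natural one for a leftover count is used here: (84 − returned)/84.

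**1. Empty return.** If nothing returned is read as zero left, the score is (84 − 0)/84 = 100% whatever was taken. A subject who took 42 pouches has a true value of 42/84 = 50%.

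**2. Doses after day 84.** Suppose the 12 weeks end on day 84 and the subject then takes one leftover pouch on each day until T2.

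| Taken by day 84 | True value | Score after 7 extra days | Score after 21 extra days |
|---|---|---|---|
| 77 | 77/84 = 91.7% | 84/84 = 100% | 100% |
| 63 | 63/84 = 75.0% | 70/84 = 83.3% | 84/84 = 100% |
| 42 | 42/84 = 50.0% | 49/84 = 58.3% | 63/84 = 75.0% |

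A full score results only when missed doses do not exceed the extra days.

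**3. How much the missing rule matters.** As an illustration only, take 14 evaluable EGCG subjects, 4 without a usable count, and 7 of the 10 counted subjects meeting some criterion. The 4, the 7 and the criterion are assumed. Intervals are exact 95%.

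- Uncounted taken as adherent: 11/14 = 78.6% (49.2 to 95.3)
- Uncounted excluded: 7/10 = 70.0% (34.8 to 93.3)
- Uncounted taken as non-adherent: 7/14 = 50.0% (23.0 to 77.0)

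The spread is 78.6 − 50.0 = 28.6 points, which is 4/14. It comes entirely from a rule that the protocol does not state for uncounted drug.

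**The case against.** A reader might infer that the pill count is the only source on adherence. It is not. The Arm 1 calls assess adherence, their log is an Aim 1 data source, and serum EGCG at T2 gives some exposure information. These do not close the gap, however. Section 5.9 describes the weekly contact as encouragement, allows email instead of a call, and specifies no dose count. The serum value is a single sample planned for after dosing has ended. Nothing says how either source enters the adherence result.

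A reader might also infer that a subject who returns nothing scores as fully adherent, and that every error pushes the estimate upward. The documents do not support that. They contain no scoring rule, and under the complete-case default in section 11.2 a subject without a count may simply be missing. An undefined measure is established; a known upward bias is not.

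A phone or Zoom T2 does not by itself prevent a return. The wording allows mixed visits, and T2 includes a research blood draw, so there is normally physical contact at which drug can be handed over. The gap is confined to a wholly remote visit.

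The late-dose figures are limits, not expectations. They require dosing on every day of a window that the protocol treats as off drug, and the larger figure requires T2 at its latest. Because the adherence criterion is undefined, it is unknown whether 92% instead of 100% would reclassify anyone.

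**Conclusion.** The point holds in this limited form. One leftover count, with supply exactly equal to scheduled doses, cannot distinguish full intake from unreturned drug and cannot show doses taken after week 12. No return or count route is described for a wholly remote T2. Aim 1 adherence may therefore be overstated or missing.

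The late-dose effect is bounded by the extra days: about 7 to 21 doses, so 92% or 75% on schedule could count as 100%. This rests on the assumed formula, one pouch a day, and the 12 weeks ending on day 84. The size of the non-return effect cannot be known in advance; the 50% to 79% range only illustrates it.

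The sample size is not affected. The change is worth making because what is not collected by T2 cannot be recovered afterwards.

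**What to change.** In sections 5.9 and 5.10:

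1. Ask subjects to return the bag with all pouches, opened and unopened. A fully adherent subject then returns 84 opened pouches, and pouches unaccounted for become visible.
2. Record the last-dose date and count doses taken within the 12-week period. For example, 84 opened pouches with a last dose on day 91 mean, at one pouch a day, at least 84 − 7 = 77 doses in the period. Expected doses should end at any stop that the protocol directs, so that such a stop is not scored as non-adherence.
3. State the formula and the adherence criterion that section 11.1 refers to.
4. Record an unreturned bag as unknown, never as zero left. Report the adherent proportion three ways: unknowns excluded, all adherent, all non-adherent. Use the weekly call log as supporting data.
5. For a wholly remote T2, use a prepaid mailer or an on-camera count.

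The cost is some wording, a few log fields and a few mailers. Opened pouches still do not prove ingestion, and the reported adherence may be lower.

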### *Exploratory Aim 3: Semi-structured interviews:*

We will conduct semi-structured interviews with subjects at the post-intervention assessment (T2). Questions in the interview will be structured in a way to gain insights into the frailty experience of older survivors of colorectal cancer post adjuvant treatment. Interviews will be audio recorded and transcribed verbatim. Interviews with the subjects will be held in person in a private space (clinic or office space). Interviews will be audio-recorded and led by study investigators and will last 30 minutes. These recordings will be uploaded to Box, and the recordings will be deleted from the audio-recorder. All interviews will be transcribed and qualitatively analyzed in an iterative process until theoretical saturation is achieved.

We will also ask subjects about the usefulness and acceptability of the study treatments during the close out interview. The post intervention visit and measures may be completed in person, via phone and/or Zoom.

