### **2.3 Study Outcomes**

***Aim 1:*** To determine the feasibility and safety of conducting a two arm RCT as measured by recruitment rate, adherence to study procedures and EGCG intervention, and adverse events.

***Aim 2:*** To obtain preliminary data on the effects of EGCG vs UC on frailty measured by FFS (weight loss, weakness measured by hand-grip dynamometry, slowness measured by 4 meter walk test, physical activity measured by the GODIN Leisure-Time Physical Activity, and exhaustion

measured by the symptom inventory) and the Deficit Accumulation Frailty Index (DAFI) based on the geriatric assessment.

**Aim 3:** To obtain preliminary data on the effects of EGCG vs UC on TNF- $\alpha$  related immune responses (measured by serum levels of TNF- $\alpha$ , TNFR I, TNFRII, IL-6, IL-1 $\beta$ , and CRP) and circulating immune cells as measured by lymphocytes, monocytes, neutrophils, total WBC, NLR, LMR in older survivors of CC.

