**Table 3: Fried Frailty Score (FFS)**

Slowness	time to walk 4 meters based on height: $\leq 0.65\text{m/s}$ for height $\leq 1.59\text{m}$ ; $\leq 0.76\text{ m/s}$ for height $>1.59\text{m}$
Weakness	grip strength/body mass index (BMI): $\leq 17$ for BMI 23-26; $\leq 18\text{kg}$ for BMI 26-29; $\leq 21\text{kg}$ for BMI $>29$
Weight loss	$>10\text{lb}$ lost unintentionally in the last year/last visit or BMI $<18.5$
Physical Activity	GODIN Leisure Score Index- Activity/week: Score $\leq 23$ equivalent to $<14\text{ Kcal/kg/week}$
Fatigue	answer yes to any of the following (low usual energy level; unusually weak or tired in the last month)

FFS will be assessed using the 5 characteristics listed in Table 3. For each characteristic, subjects will receive a score of one if they met the cut-off for that characteristic. The scores will be summed. Total scores can range from zero to five to represent FFS, with zero indicating that they did not

meet any cut offs, and five meaning that they met all five cut offs. FFS was chosen because it can quickly assess frailty in outpatient settings, has good construct, convergent, concurrent, and predictive validity, and is sensitive to change following an intervention. Subjects can be classified into three frailty groups based on the FFS: FFS= 0 is classified as robust/not frail, FFS= 1 or 2 classified as pre-frail, and FFS= 3-5 classified as frail.

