## **5.6 Randomization**

Randomization will be revealed to the subject at the end of the baseline assessment and immediately before delivering the study drug.

We will employ two arms in a 1:1 allocation ratio:

1. EGCG: 12 weeks daily of 800mg EGCG +250mg VitC taken 1 time a day at breakfast (four 200mg EGCG capsules will be packaged with one 250mg VitC tablet)
2. Usual care

Consented subjects will be randomized with a computer-generated random numbers table with block sizes of 2. We will stratify by race (Black vs other) and treatment type (surgery vs other).

The random numbers tables will be generated centrally using software provided by [name], the project biostatistician. A total enrollment of 40 subjects is planned. Due to the study design the PI, study subjects, personnel, and statisticians will be un-blinded to the treatment assignments.

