## **11.2 Statistical analysis**

**Quality control.** We will use electronic forms and audit our database. We will visually inspect all data. The distribution of the data will be examined. If deviations from statistical assumptions are detected, appropriate statistical steps (e.g., transformation, non-parametric analysis, missing data sensitivity analysis) will be applied. To follow the "intent-to-treat" principle, patients will be analyzed according to randomization. Since this is a small feasibility trial, study hypotheses will be tested at  $\alpha=0.15$  (2-tailed significance level). We will work closely with [name] (biostatistician).

**Missing data.** Every effort will be made to facilitate the subjects' completion of questionnaires and comprehensive collection of data. If there are missing data, reasons for missing data will be recorded, tabulated and reported based on treatment group. Differences in patterns of missing data

between treatment groups will be compared. Special considerations will be given to missing data for inflammatory biomarkers. If inflammatory biomarker data are missing due to lower limit of detection, we will use the appropriate imputation method. Otherwise, since this is a small study, we will report the complete case analysis. We will use the information about missing data when assessing feasibility.

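### T2 may be done remotely, but the FFS needs a grip test and a timed 4-meter walk, and the plan has no rule for an FFS with an unmeasured item

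*Combined protocol and SAP*

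**What the plan says.** - **Mode of T2.** Section 5.10 has T2 follow the baseline format and adds the Fried measures taken at screening. The end of its interview subsection states: "The post intervention visit and measures may be completed in person, via phone and/or Zoom". Section 5.5 is narrower for baseline, where only some measures may be remote.
- **How the items are measured.** Section 2.3, Aim 2, specifies "weakness measured by hand-grip dynamometry, slowness measured by 4 meter walk test". Section 5.4, Table 3, sets cut-offs for both. No remote procedure is described for either. Section 5.1 foresees virtual versions of some assessments and gives the SPPB and MoCA as examples. The SPPB in Section 5.5 contains a 3-meter walk.
- **Scoring.** Section 5.4: "For each characteristic, subjects will receive a score of one if they met the cut-off for that characteristic. The scores will be summed". A total of zero is defined as meeting no cut-off. An item that was not tested is not mentioned.
- **Missing data.** Apart from biomarkers below the detection limit, Section 11.2 says: "Otherwise, since this is a small study, we will report the complete case analysis". It does not say whether an FFS with four of five items counts as complete.
- **Blinding.** Section 5.6: "the PI, study subjects, personnel, and statisticians will be un-blinded".

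**The concern.** As written, the permission lets the one powered efficacy outcome go partly unmeasured, and the plan does not say what to do then. Two analysts could follow the text faithfully and give the same subject different results: one a sum of the items available, the other a missing score.

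Each choice has a cost. Dropping the score removes subjects from a comparison planned on 14 per arm. Summing what is available can only lower a remote score, because an untested item cannot add a point. That would look like improvement from an entry score that must be at least 2. Section 11.1 intends to use the means, variances and pre-post correlation to size the next trial, so a shift shared by both arms would still damage those planning figures.

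Unequal remote use is plausible. The trial is open-label, only EGCG subjects return pills at T2 and have liver tests at weeks 4 and 8, and no criterion is given for choosing the mode.

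**Working it through.** **1. The plan's own power (Section 11.1).** Inputs: 14 evaluable per arm (70% of 20), two-sided α = 0.15 (Section 11.2), effect 0.66 SD, pre-post correlation 0.5, ANCOVA with baseline FFS.

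- Residual SD = √(1 − 0.5²) = 0.866
- SE = 0.866 × √(2/14) = 0.327
- 0.66 / 0.327 = 2.016; critical value 1.440
- Power = Φ(2.016 − 1.440) = 0.718 by the normal approximation; 0.704 by noncentral t with 25 df

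The stated 70% reproduces.

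**2. If an FFS with an unmeasured item is missing.** Assume a share r of the 14 completers in each arm is remote and loses the FFS. The remaining n is rounded down, and power uses noncentral t with 2n − 3 df.

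| r (assumed) | FFS values per arm | Power |
|---|---|---|
| 0% | 14 | 0.70 |
| 10% | 12 | 0.65 |
| 20% | 11 | 0.62 |
| 30% | 9 | 0.55 |
| 50% | 7 | 0.47 |

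This loss comes on top of the 70% completion target, since a remote subject can complete the study without an FFS. Keeping 14 FFS values per arm needs 14/(1 − r) completers: 15.6, so 16 of 20 (80%) at r = 10%; 17.5, so 18 of 20 (90%) at r = 20%; and all 20 at r = 30%.

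**3. If the available items were summed.** False mean change within an arm = −r × (sum of the T2 prevalences of the unmeasured items). The documents give neither r nor the prevalences, so take r = 10% to 50% and each item positive in 30% to 70%:

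- Grip and walk both lost: from −0.10 × 0.6 = −0.06 to −0.50 × 1.4 = −0.70 points
- Grip only lost: from −0.10 × 0.3 = −0.03 to −0.50 × 0.7 = −0.35 points

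For example, an unchanged subject who is slow, weak and fatigued has FFS 3. Under this reading the score would be 2 with grip untested and 1 with both untested.

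**4. Effect on the arm contrast.** The planned ANCOVA was simulated with no treatment effect: 14 per arm, entry FFS ≥ 2, 4,000 runs, nominal α = 0.15. The assumed item model gives T2 prevalences of about 0.46 (slow) and 0.52 (weak). Bias is EGCG minus usual care, in FFS points.

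| Handling | Remote, EGCG vs usual care | Bias | Type I error |
|---|---|---|---|
| Sum, both items lost | 30% vs 30% | 0.00 | 0.147 |
| Sum, both items lost | 30% vs 0% | −0.29 | 0.265 |
| Sum, both items lost | 20% vs 50% | +0.29 | 0.264 |
| Sum, grip only lost | 30% vs 0% | −0.16 | 0.192 |
| Missing, complete case | 30% vs 0% | +0.02 | 0.152 |

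The complete-case row assumes that remote use is unrelated to frailty. If the frailest subjects were the least able to attend, that assumption would fail.

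**The case against.** The strongest reply has four parts.

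- **The complete-case rule already points to missing.** A reader might infer from the summing sentence that an untested item counts as zero. The documents do not say so: "subjects will receive a score of one if they met the cut-off for that characteristic" describes a test result, and Section 11.2 leans towards dropping an incomplete score. This stands. What remains is that no sentence defines when an FFS is incomplete, and that dropping it costs power.
- **A remote FFS need not lose both items.** It would be tempting to say that a remote score cannot exceed 3. That does not follow, because a virtual SPPB with a timed walk is foreseen. The inference is firm for grip and weaker for the walk, although the SPPB walk is 3 meters and the FFS walk is 4.
- **A fully remote T2 is unlikely.** Both arms have a T2 blood draw, and Section 5.1 says equipment needs bring some assessments into the laboratory. The interviews are also to be held in person. This lowers the likely share but does not exclude it. Section 5.5 allows the draw at an affiliated lab or medical office, where no grip or walk test is specified.
- **No direction of bias is fixed.** If pill return brings EGCG subjects in, usual care would have more remote visits, and summing would work against EGCG. With equal shares, the null contrast is unbiased. Both statements are correct, so no single bias figure can be attached to the plan.

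Section 11.2 also requires reasons for missing data to be reported by arm. That covers part of the remedy, but not visit mode.

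**Conclusion.** The point holds as a gap between a stated permission and the measurements that the FFS requires. Remote T2 is allowed without exception, no remote method is given for grip or the 4-meter walk, and the handling of a partly measured FFS is undefined.

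If such scores are missing, power falls from about 0.70 to 0.65, 0.62 and 0.55 at 10%, 20% and 30% remote. This assumes equal shares in both arms and retention at the 70% target; better retention would offset some of it. If available items were summed, the pre-post change would be biased downward, and the arm contrast would be biased in either direction when shares differ. Those sizes rest on assumed shares and prevalences, and the plan does not prescribe that scoring.

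This is a feasibility trial seeking preliminary estimates, so the issue is not fatal. It should still be corrected, because those estimates will inform the next trial and the correction is cheap.

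**What to change.** - **Section 5.10:** exempt grip strength and the 4-meter walk from the remote option. Do both in person at T2, tied to the blood draw planned for both arms. Other measures may stay remote.
- **Sections 5.4 and 11.2:** state that an unmeasured FFS item is missing, never 0, and that the FFS total is then missing.
- **Data collection:** record visit mode at T0 and T2 and tabulate it by arm.

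The cost is a few sentences and perhaps a few rescheduled visits, for which Section 5.2 allows up to three weeks after the end of study drug. Draws at outside labs or medical offices would need coordination so that the two tests can be done. Section 5.4 puts the whole Fried measure at 5 to 10 minutes. A few FFS values may still be missing, but they would be visible as missing.
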